2.2 Endpoints

2.2.1 Primary Endpoint

The primary endpoint of this trial is the overall graft survival, evaluated at Year 3

2.2.2 Secondary Endpoints

Secondary endpoints of this trial are:

- Overall graft survival evaluated at Year 1 and 2
- Patient survival, evaluated at 3 years after start of treatment in feeder trial
- Kidney function, as evaluated by eGFR, S/P-creatinine and albumin/creatinine ratio in urine at 1, 2, and 3 years after start of treatment in feeder trial
- Proportions of subjects with presumed or biopsy proven AMR episodes (classified according to Banff 2017 or later version) within 3 years after start of treatment in feeder trial
- Proportion of subjects with presumed or biopsy-proven rejection episodes, (other than AMR episodes) (classified according to Banff 2017 or later version) up to 3 years after start of treatment in feeder trial
- DSA levels at 1, 2, and 3 years after start of treatment in feeder trial
- Anti-imlifidase IgG at 1, 2, and 3 years after start of treatment in feeder trial

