7. TRIAL ASSESSMENTS

7.1 Assessments related to Primary Endpoint

The primary endpoint of this trial is to determine the overall graft survival, defined as time from start of treatment (imlifidase or plasma exchange) of active or chronic active AMR in feeder trial to graft loss, evaluated at year 3. Graft loss is defined as permanent return to dialysis for at least 6 weeks, re-transplantation, or nephrectomy. The date of graft loss will be recorded. If dialysis is used to define graft loss, the date of graft loss is the first day of the dialysis period defining the graft loss.

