12.4.4 Proportion of subjects with rejection episodes

Proportion of subjects with presumed or biopsy-proven AMR episodes (classified according to Banff 2017 or later) and proportion of subjects with biopsy-proven rejection episodes, (other than AMR episodes) within 3 years after start of treatment in feeder trial will be listed and summarised by treatment group.

12.4.5 DSA level at 1, 2, and 3 years after start of treatment in feeder trial

DSA levels (measured using SAB-HLA assay) 1, 2 and 3 years after start of treatment in feeder trial will be summarized, listed, and presented graphically.

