3.1 Full analysis set

The Full Analysis Set will be defined as all patients enrolled in 20-HMedIdeS-18. Because of the observational nature of this trial no other analysis set will be defined, and all data presentations and all outputs will be based on the FAS.

4 Statistical analyses and presentation of data

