4.4.2.4 Proportion of patients with rejection episodes

Proportion of patients with presumed or biopsy-proven AMR episodes (classified according to Banff 2017 or later) and proportion of patients with biopsy-proven rejection episodes, (other than AMR episodes) within 3 years after start of treatment in feeder trial will be listed and summarised by treatment group.

4.4.2.5 DSA level at 1, 2, and 3 years after start of treatment in feeder trial

DSA levels (measured using SAB-HLA assay) at 1, 2 and 3 years after start of treatment in the feeder trial will be summarized, listed, and presented graphically. The individual plots, will include sum of DSA as a separate line. Mean plots will display the mean of "sum of DSA".

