9.1 Tables

Table 14.1.1 Patient disposition, including reason for discontinuation (All screened patients).

Table 14.1.2 Protocol Deviations (FAS).

Table 14.1.3 Demography and body measurements (FAS).

Table 14.1.4 Medical and surgical history (FAS).

Table 14.1.5 Concomitant medication (FAS).

Table 14.1.6 Previous transplant kidney history (FAS).

Table 14.2.1 MFI levels for DSA – by time point (FAS).

Table 14.2.2 Kidney function (based on S/P-creatinine analysis) (FAS).

Table 14.2.3 Proportion of patients with absence of graft loss at 1 year, 2 years and 3 years (FAS)

Table 14.2.4 Proportions of patients with presumed or biopsy proven AMR episodes (FAS).

Table 14.2.5 Proportion of patients with presumed or biopsy-proven rejection episodes, (other than AMR episodes) (FAS).

Table 14.2.6 Total IgG – by timepoint (FAS).

Table 14.2.7 Proportion of patients having reduction in total IgG (FAS).

Table 14.2.8. Patient survival (FAS)

Table 14.3.1 Overview of AEs (FAS).

Table 14.3.2 Summary of AEs – by SOC and PT (FAS).

Table 14.3.3 Summary of AEs – by causality (FAS).

Table 14.3.4 Summary of AEs – by severity (FAS).

Table 14.3.6 Summary of SAEs (FAS).

Table 14.3.7 Summary of SAEs – by causality (FAS).

Table 14.3.10 Summary of SAEs leading to death (FAS).

Table 14.3.11 Summary of SAEs leading to withdrawal (FAS).

Table 14.4.1 Summary of clinical chemistry variables (U-Albumin, Creatinine, U-Albumin/creatinine ratio) – by time point (FAS).

Table 14.4.2 Anti imlifidase IgG (ADA) (mg/mL) – by time point (FAS)

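### The 3-year rejection proportions have no rule for follow-up that ends early, which biases them down, and graft loss or death without a recorded episode can hide AMR differences between arms

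*Protocol*

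**What the plan says.** Protocol 2.2.2 makes both rejection endpoints proportions over a fixed window. For AMR the measure is "Proportions of subjects with presumed or biopsy proven AMR episodes (classified according to Banff 2017 or later version) within 3 years after start"; the clock begins with feeder-trial therapy, and rejection other than AMR is worded in parallel. The planned analysis is one sentence in Protocol 12.4.4, repeated in SAP 4.4.2.4: the proportions "within 3 years after start of treatment in feeder trial will be listed and summarised by treatment group".

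The denominator comes from SAP 3.1: "The Full Analysis Set will be defined as all patients enrolled in 20-HMedIdeS-18". No other set exists, and "all data presentations and all outputs will be based on the FAS". Tables 14.2.4 and 14.2.5 carry the FAS label.

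Neither document defines time at risk, censoring, competing events or evaluability for rejection. The general rule in SAP 4.1.4 leaves missing values unadjusted; its exceptions concern adverse-event fields and partial dates. Graft survival, by contrast, is analysed by Kaplan-Meier with a censoring rule (Protocol 12.3.1, SAP 4.4.1), and SAP 4.4.2.2 extends Kaplan-Meier to patient survival. SAP section 6 records that the study was stopped early in January 2023. The SAP, effective 12 May 2023, keeps the 3-year proportion without adjustment.

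**The concern.** Rejection of the treated graft can be recorded only while the patient is alive, followed and still has that graft. With an event-only numerator, an all-enrolled denominator and no further rule, anyone who leaves observation without a recorded episode is by default a patient without rejection for 3 years. Two different problems follow.

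The first is incomplete follow-up. Withdrawal and the early termination hide later episodes, so the proportion understates 3-year occurrence.

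The second is removal from risk. Graft loss or death without a recorded episode ends the chance of a later one. An arm with more such losses can therefore show a lower AMR proportion when the AMR rate is the same in both arms. AMR is the disease that was treated, and the results are shown by arm, with 95% confidence intervals under SAP 4.1.1. Readers will compare the arms even without a test.

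**Working it through.** The documents give no AMR, graft-loss, death or withdrawal rate, and no power or sample-size calculation for this endpoint, so there is no planned figure to reproduce. Their only relevant number is the anticipated 20 imlifidase and 10 plasma exchange patients (Protocol 12.6). All hazards below are assumptions.

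**Model.** Constant yearly hazards: *a* for AMR, *m* for graft loss or death without a prior recorded episode, *w* for withdrawal.

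- Raw 3-year proportion = a/(a+m+w) × (1 − exp(−3(a+m+w)))
- Composite of AMR, graft loss or death = 1 − exp(−3(a+m))

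**1. Withdrawal** (a = 0.20, m = 0.05)

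| w | Calculation | Raw proportion |
|---|---|---|
| 0 | 0.20/0.25 × (1 − exp(−0.75)) | 42.2% |
| 0.05 | 0.20/0.30 × (1 − exp(−0.90)) | 39.6% |
| 0.10 | 0.20/0.35 × (1 − exp(−1.05)) | 37.1% |
| 0.20 | 0.20/0.45 × (1 − exp(−1.35)) | 32.9% |

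The quantity sought is 42.2% in every row. The shortfall comes only from treating withdrawn patients as non-events.

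**2. Early termination.** Protocol 3.2 puts the first feeder-trial treatment about October 2019, some 39 months before January 2023. Only patients treated in the first 39 − 36 = 3 months could reach a full 3 years. With uniform accrual over an assumed 9 to 30 months, that is 3/9 = 33% down to 3/30 = 10% of patients. With a = 0.20 and no other exits, the 3-year value is 1 − exp(−0.60) = 45.1%. Averaging 1 − exp(−0.20 × available years) over accrual gives an observed 43.2% down to 32.1%.

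**3. Graft loss or death** (a = 0.20 in both arms, w = 0)

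| m | Raw AMR proportion | Composite |
|---|---|---|
| 0.05 | 0.20/0.25 × (1 − exp(−0.75)) = 42.2% | 1 − exp(−0.75) = 52.8% |
| 0.20 | 0.20/0.40 × (1 − exp(−1.20)) = 34.9% | 1 − exp(−1.20) = 69.9% |

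The arm with four times the loss shows 7.3 points less AMR, yet is 17.1 points worse on the composite.

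**4. Range.** With exits rising from 0 to 0.50 per year, the raw proportion falls from 25.9% to 13.9% at a = 0.10, from 45.1% to 25.1% at a = 0.20, and from 59.3% to 34.1% at a = 0.30. An arm with the higher AMR hazard (0.25 v 0.20) shows the lower raw proportion once its exit hazard exceeds about 0.18 against 0.05.

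**5. At the trial's size** (assumed counts; episodes at a mean of 1.5 years, losses at 0.75). Arm A has 20 patients, 6 with AMR and 8 with episode-free graft loss or death. Arm B has 10 patients, 4 with AMR and 1 such loss.

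- Raw: 6/20 = 30% v 4/10 = 40%.
- Graft-years at risk: A 6×1.5 + 8×0.75 + 6×3 = 33; B 4×1.5 + 1×0.75 + 5×3 = 21.75. AMR per 100 graft-years: 18.2 v 18.4.
- Composite: 14/20 = 70% v 5/10 = 50%.

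**6. What each remedy repairs.** The raw formula with w = 0 is itself the cumulative incidence with graft loss and death as competing events. With nobody censored, Aalen-Johansen returns the same 42.2% and 34.9%. It repairs items 1 and 2 but leaves item 3 unchanged; only the composite shows item 3.

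**The case against.** The strongest case against is that a crude proportion with an episode is a legitimate summary for a secondary, untested endpoint in at most 30 patients, and that the remaining outputs supply the context. Much of this stands.

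- **Other outputs.** Table 14.2.3 (graft loss), Table 14.2.8 (patient survival), Table 14.1.1 (disposition) and the patient listings let a reader reconstruct episode-free exits. It would be wrong to say the information is absent. It is not brought together where AMR is reported.
- **Losses caused by AMR.** Presumed AMR counts, and reason and root cause of graft loss are recorded (Protocol 6.1.2), so many such losses may already be in the numerator. The concern covers only exits without a recorded episode.
- **Size.** The 7.3-point gap is less than one patient in an arm of 10 and about 1.5 in an arm of 20.

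Some stronger readings are tempting but unsupported. A reader might infer that the plan declares early leavers rejection-free. It does not: this is the default left by silence, and SAP 4.1.4 could even be read as dropping them, which would bring its own selection. A reader might also infer that rejection of a second graft would be counted, because "Graft loss is defined as permanent return to dialysis for at least 6 weeks, re-transplantation, or nephrectomy". Neither document says whether visits continue after a later graft loss, or which graft the count refers to. Nor is a patient who loses the graft at, say, month 8 a safe example. Under Protocol 3.1, those who lose it before they can enter do not continue, and Protocol 6.1.1 allows entry up to Year 1 plus 2 months, so that patient may not be in the FAS.

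**Conclusion.** The concern holds in two parts. First, patients without a recorded episode whose follow-up ends through withdrawal or the January 2023 stop default to non-events, so the 3-year rejection proportion is biased down. In the withdrawal illustration it falls from 42% to between 40% and 33%; in the termination illustration, from 45% to between 43% and 32%. Second, graft loss or death without a recorded episode can make an arm with more losses show less AMR at equal AMR rates: 42% v 35%, with the composite at 53% v 70%.

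The direction of the first part needs only that some patients leave early and would have had an episode later. Its size, and the whole of the second part, rest on assumed constant hazards, and the second also needs unequal loss between arms. The documents do not support a prediction that this will happen, or that one named arm will benefit. The matter is worth correcting because the correction is cheap, but its weight is moderate: the endpoint is secondary and descriptive, and the study is small.

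**What to change.** Amend SAP 4.4.2.4 and Tables 14.2.4 and 14.2.5 as follows.

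1. Report by arm the Aalen-Johansen cumulative incidence of first rejection at Years 1, 2 and 3, for AMR and for other rejection. Count only the graft treated in the feeder trial, treat graft loss and death as competing events, and censor at last contact or study termination. State that this corrects incomplete follow-up only, and that it assumes censoring is unrelated to rejection risk.
2. To expose the graft-loss effect, show beside it by arm 1 minus Kaplan-Meier for the composite of rejection, graft loss or death, and the number of episode-free exits by reason (graft loss, death, withdrawal, termination).
3. Keep the raw count as a descriptive line.
4. Where no onset date is recorded, date the episode from the biopsy or the start of rejection treatment.
5. State that the estimates apply to patients who entered the follow-up trial, because entry comes after treatment start and early graft losers may not enter.

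The cost is SAP wording, a few lines of programming and some derivation of dates. Graft-loss and death dates are required. The withdrawal date is recorded only if possible (Protocol 4.5), and no rejection-onset date is named. With at most 30 patients the intervals will be wide.

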3. INVESTIGATIONAL PLAN

3.1 Overall Trial Design

This is an observational 3-year follow up trial. Trial sites that have participated, or are currently participating, in trial 16-HMedIdeS-12 (the “feeder trial”) will be contacted and requested to approach subjects for enrolment in the trial. Up to 30 subjects will be included depending on subjects’ willingness to participate in the trial. Subjects who lose their graft during the feeder trial or in the intermediate time before being able to enter this trial will not continue in the trial but information about the graft loss will be collected.

The trial will primarily evaluate graft survival. The subjects will attend 3 follow up visits 1, 2 and 3 years after start of treatment in the feeder trial. Signing of Informed Consent may be performed any time between last visit in the feeder trial and up to first visit in the follow up trial.

Kidney function and patient survival will be assessed. Graft rejection episodes will be determined using classification according to Banff 2017 or later version. Information from kidney biopsies performed within standard of care will be collected. Blood samples for analysis of DSA and ADA will be collected at each visit. Medically relevant comorbidity (infections, malignancy, diabetes mellitus, cardiovascular events and comorbidity leading to worsening of kidney function), will be recorded. Information about treatments of graft rejection episodes will be recorded (e.g. plasma exchange and IVIg) as well as creatinine-level and DSA data conducted within standard of care due to the graft rejection episode.

If a planned visit cannot be performed, subjects may be contacted by phone and assessments described in this protocol may be collected from a local laboratory.

The overall trial outline is summarized in [Figure 1](#).

Figure 1. Overall trial design.

3.1.1 Medical monitoring

Medical monitoring will be performed at an interval described in the Medical monitoring plan.

3.1.2 Interim Analysis

No interim analysis is planned but reports may be created if judged needed.

3.2 Trial Schedule

The first subject first visit is planned in October 2020, 1 year after first subject was treated in the feeder trial.

Last subject last visit in this trial will be 3 years (+/- 4 months) after last subject's first visit in the feeder trial.

3.3 Planned Number of Trial Sites and Subjects

All sites included in the feeder trial, approximately 14 sites, in US, Europe and Australia, will be asked to participate, and up to 30 subjects may be included.

3.4 End-of-Trial

The planned End-of-Trial is defined as last subject last visit. Hansa Biopharma will ensure that an End-of-Trial Notification is submitted to the concerned health authority and IEC/IRB according to local requirements.

For procedures in case of premature termination or suspension of the Trial, see Section [13.4](#).

4. TRIAL POPULATION

4.1 Eligibility Criteria

Subjects who have been treated with imlifidase or plasma exchange in the feeder trial may be included. The subjects will be approached, and informed consent will be obtained for participation in the current trial.

The investigator will maintain a screening log to record details of all subjects screened and to confirm eligibility or record reasons for screening failure, as applicable. Confirmed eligibility or reasons for screening failure will be recorded in the eCRF.

4.2 Inclusion Criteria

- Signed Informed Consent obtained before any trial-related procedures
- Willingness and ability to comply with the protocol
- Previous treatment with imlifidase or plasma exchange in the trial 16-HMedIdeS-12

Note: The primary objective of this trial is overall graft survival after treatment with imlifidase or plasma exchange. Therefore, subjects can also be included even if the subject did not fully complete the feeder trial follow up but was dosed with imlifidase or plasma exchange in the trial 16-HMedIdeS-12.

4.3 Exclusion Criteria

- Inability by the judgement of the investigator to participate in the trial for any other reason

4.4 Restrictions

4.4.1 Prohibited Therapy

Subjects will continue with their prescribed therapies (drugs or procedures) during the trial.

4.5 Discontinuation of Subjects

The subjects have the right to withdraw from the trial at any time for any reason, without the need to justify their decision. However, the investigator should record the reason and date for the subject's withdrawal, if possible. The investigator also has the right to withdraw subjects. In either event, the investigator must notify the Monitor.

A subject that prematurely discontinues participation will, if possible, be called in for an End-of-Trial Visit (as defined in Visit Procedures, Section 6.1.2). Even if the subject is not able to attend, the End-of-Trial Form must be completed.

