6. TRIAL PROCEDURES

6.1 Trial Visits

The flow chart of all trial visits, including applicable visit windows, is provided in Section 6.2. A list of scheduled activities/assessments for each visit is provided in Sections 6.1.1 to 6.1.2 and further details of how each activity/assessment is to be performed is given in the subsections to Section 7.

All subjects considered for the trial must be informed about the trial, verbally and in writing, and give their written consent before any trial procedure is performed.

Informed consent may be signed at the last visit in the feeder trial. For each subject, the duration of the trial, including the time from signing informed consent to end of trial will not exceed 3 years and 10 months. This includes 6 months if informed consent is signed at the end of trial in feeder trial and the visit window of 4 months at Year 3 visit.

If a subject is not able to attend a planned visit, the subject may be contacted by phone and assessments described in this protocol may be collected from a local laboratory.

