12.3.1 Primary efficacy analysis

Overall graft survival at Year 3. Graft survival is defined as time from start of treatment (imlifidase or plasma exchange) of active or chronic active AMR in feeder trial to graft loss, evaluated at year 3. Graft loss is defined as permanent return to dialysis for at least 6 weeks, re-transplantation, or nephrectomy. If dialysis is used to define graft loss, the date of graft loss will be the first day of the last ongoing dialysis period reported.

The primary endpoint will be analysed by the Kaplan-Meier survival method. The overall graft survival will be tabulated and presented graphically with 95% confidence limits by treatment.

The following events will be censored at the time of occurrence: withdrawal from the trial without graft loss, evaluation time point and end of trial without graft loss.

The reason for graft loss will be tabulated by time.

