2.3 Blinding

The study is an open-label study. The study is fully unblinded.

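### No graft or vital status is planned after a subject withdraws or is withdrawn, so later graft losses go uncounted and censoring at withdrawal may be informative

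*Protocol*

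**What the plan says.** Protocol 4.5 allows a subject to leave at any point without giving a reason, and continues: "The investigator also has the right to withdraw subjects". No criterion is attached to the investigator's right. On recording, it says: "However, the investigator should record the reason and date for the subject's withdrawal, if possible". On the final assessment: "A subject that prematurely discontinues participation will, if possible, be called in for an End-of-Trial Visit". By Protocol 6.1.2 that visit includes graft and patient survival status. Section 4.5 ends: "Even if the subject is not able to attend, the End-of-Trial Form must be completed". The content of the form is not given.

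Protocol 12.3.1 lists the reasons for censoring graft survival as "withdrawal from the trial without graft loss, evaluation time point and end of trial without graft loss", and SAP 4.4.1 repeats the list. For patient survival, Protocol 12.4.2 plans a listing and a summary. SAP 4.4.2.2 adds a Kaplan-Meier analysis but no censoring rule. SAP 4.1.4 leaves missing data missing, with exceptions only for adverse-event attributes and for adverse-event and medication dates. No sensitivity analysis for withdrawal is planned.

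A subject who stays enrolled but misses a visit is treated differently. Protocol 3.1 says: "If a planned visit cannot be performed, subjects may be contacted by phone", with assessments obtainable from a local laboratory, and Protocol 6.1 repeats this. SAP 2.3 states: "The study is fully unblinded".

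**The concern.** The trial exists to measure Year 3 graft survival, and patient survival is a secondary endpoint. No trial treatment is given (Protocol 5), so withdrawal stops only observation. Yet formal withdrawal ends the collection of the outcome itself.

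Graft loss is defined in Protocol 7.1 by lasting dialysis, re-transplantation or nephrectomy. These events, like death, can normally be established from the medical record without a trial visit. The protocol already uses that record for comorbidity (7.2.7) and for standard-of-care biopsies (6.2), so nothing in the design requires outcome collection to end at withdrawal.

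Kaplan-Meier treats a censored subject as having the same future risk as those still followed. If subjects with failing grafts or declining health tend to leave, or are withdrawn by an investigator who knows the feeder arm, the curve is too high, possibly by different amounts in the two arms. With about 20 and 10 subjects, one or two such cases matter.

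**Working it through.** **Inputs.** From the documents: about 20 imlifidase and 10 plasma exchange subjects (Protocol 12.6; 20 + 10 = 30), Kaplan-Meier, and censoring of graft survival at withdrawal. There is no power calculation, withdrawal rate or event rate to reproduce. Assumed: Year 3 Kaplan-Meier graft survival S of 70% to 90%; a fraction p of subjects with a functioning graft withdrawing at 18 months; and a graft-loss hazard multiplied by k after withdrawal.

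**Bias under a constant hazard.** Let s = √S, the survival to 18 months. Kaplan-Meier, using only subjects under follow-up, converges to S. True survival is

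s × [(1 − p) × s + p × s^k].

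With k = 1 this is s² = S, so there is no bias for any p.

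For S = 80%, s = 0.8944:
- p = 10%, k = 2: 0.8944 × (0.9 × 0.8944 + 0.1 × 0.8000) = 0.792.
- p = 20%, k = 3: 0.8944 × (0.8 × 0.8944 + 0.2 × 0.7155) = 0.768.
- p = 30%, k = 5: 0.8944 × (0.7 × 0.8944 + 0.3 × 0.5724) = 0.714.

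Overstatement in percentage points, by the same formula:

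| Assumed p and k | S = 90% | S = 80% | S = 70% |
|---|---|---|---|
| any p, k = 1 | 0 | 0 | 0 |
| 10%, k = 2 | 0.5 | 0.8 | 1.1 |
| 20%, k = 3 | 1.8 | 3.2 | 4.2 |
| 30%, k = 5 | 5.1 | 8.6 | 10.7 |

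A simulation with withdrawals spread over the three years, 1,000,000 subjects per scenario, gives nearly the same: 0.9, 3.2 and 8.6 points at S = 80%.

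**Bounds without a hazard assumption.** Suppose w subjects withdraw early, e losses are then observed among the other n − w, and all of those are followed to Year 3. Kaplan-Meier gives 1 − e/(n − w). The truth lies between 1 − (e + w)/n (all withdrawn subjects lose the graft) and 1 − e/n (none does), a width of w/n.

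| n | e | w | Kaplan-Meier | Possible range |
|---|---|---|---|---|
| 10 | 2 | 1 | 1 − 2/9 = 77.8% | 70% to 80% |
| 10 | 2 | 2 | 1 − 2/8 = 75.0% | 60% to 80% |
| 20 | 4 | 1 | 1 − 4/19 = 78.9% | 75% to 80% |
| 20 | 4 | 2 | 1 − 4/18 = 77.8% | 70% to 80% |

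Each unknown status adds 1/10 = 10 points of width in the smaller arm and 1/20 = 5 points in the larger. The Kaplan-Meier figure can be wrong in either direction within these bounds.

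**The case against.** The strongest reply is that the plan does more than a quick reading of 4.5 suggests. A reader might infer that collection ends as soon as a subject stops attending. The text does not support that: "If a subject is not able to attend a planned visit, the subject may be contacted by phone" (Protocol 6.1), and graft and patient survival are scheduled at every visit. The provision is optional and does not name graft or vital status, but it partly covers subjects who only miss visits. Status up to discontinuation is also sought at the closing visit, and the form is mandatory. The gap is confined to what happens after formal withdrawal.

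A reader might also infer that investigators could remove subjects selectively by arm. Nothing in the documents shows this. Protocol 4.5 requires the Monitor to be told, and Protocol 12.2.1 and SAP 4.2 tabulate withdrawals by arm and reason, so an imbalance would be visible. That safeguard stands, but a table of withdrawals does not recover an outcome.

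Two further points carry weight. The consent form was not available for this review, so it may already permit record use after withdrawal; even then, neither the protocol nor the SAP uses that permission. And SAP 6 records that the sponsor ended the trial in January 2023. With first treatment about October 2019 (Protocol 3.2), subjects treated after about January 2020 could not complete three full years. This is a separate source of censoring. It limits how much follow-up can be recovered and means the three-year calculations describe the design as planned. It does not supply the outcomes of subjects who withdrew earlier.

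**Conclusion.** The point holds for formal withdrawal, whether by the subject or by the unblinded investigator. Later graft losses are excluded from the primary analysis by rule, and later deaths are not collected. The censoring may be informative.

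It would be too strong to say that both survival curves are informatively censored. The documents give no reasons for leaving and no prognosis afterwards, and the bias is zero if the two are unrelated. The withdrawal-censoring rule is written for graft survival only. For patient survival the gap is that no censoring rule is stated, and no bias has been calculated for that endpoint.

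On the assumptions shown, the overstatement of Year 3 graft survival at 80% runs from 0 through about 1 and 3 points to about 9. The 9-point case needs 30% withdrawal and a fivefold hazard. The bounds of 10 and 5 points per unknown subject need only the anticipated arm sizes. The trial is descriptive, so no test is affected; the reported survival estimates are. The change should be made, because it protects the primary endpoint at little cost.

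**What to change.** - In Protocol 4.5, separate stopping trial visits from withdrawing consent to the use of medical records. Let investigator-initiated withdrawal end visits only.
- For subjects who have not withdrawn consent to record use, keep recording graft status (date and reason of loss) and vital status (date and cause of death) by phone or from the medical record at Years 1, 2 and 3, or up to trial end if earlier.
- In Protocol 12.3.1 and SAP 4.4.1 and 4.4.2.2, include these outcomes in the Kaplan-Meier analyses of graft and patient survival. Censor at last known status only where consent is withdrawn or status cannot be obtained, and write this rule out for patient survival too.
- Where status remains unknown, report the best-case and worst-case bounds beside the Kaplan-Meier estimate.

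The cost is revised wording in 4.5 and in the consent form, and a small site workload for a few of at most 30 subjects. Since the trial has closed, any retrospective status check would depend on existing consent and the necessary approvals. The bounds need only the data already held.
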